8.3.2. Sensitivity Analysis

A sensitivity analysis based on 4-component DAS28-hsCRP (as calculated in [Section 8.1.1](#)) will be performed using ITT set restricted to subjects who completed consistently the subject global assessment of disease activity.

The ACR responses will also be analyzed based on the mITT set, where NRI method (refer to protocol Appendix 13.4) will be used to impute missing value. The same statistical analysis method will be used as described in [Section 8.3.1](#). The analysis will be restricted to subjects who completed subject global assessment of disease activity consistently, as well as physician global assessment of disease activity and subject assessment of arthritis pain.

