7.7.4 Analysis of Secondary Endpoints

For secondary endpoints, change from baseline will be analyzed at Weeks 2, 4, 8, and 12 using a mixed model repeated measures (MMRM) analysis. The Chi-square tests will be used to compare the ACR20, ACR50, and ACR70 rates between the active treatment and placebo groups at Weeks 2, 4, 8, and 12. The median hsCRP will be summarized descriptively.

The DAS28-related secondary endpoint is based on 3 individual components including TJC, SJC and hsCRP (see calculation in Appendix 13.6). Sensitivity analyses based on the 4-component DAS28-hsCRP (consisting of 4 individual components including TJC, SJC, hsCRP, and subject's global assessment of disease activity [VAS]; see calculation in Appendix 13.6) will be performed using the ITT set restricted to subjects who consistently completed the subject's global assessment of disease activity reverse VAS scale.

All secondary endpoints will be analyzed using the ITT and PP analysis sets. The ACR20, ACR50, and ACR70 will be also analyzed using the mITT set, where results for subjects that are missing at the relevant visit will be imputed using nonresponder imputation (NRI).

For analyses on ACR responses (ACR20, ACR50 and ACR70) described above, the analysis will be performed on the subjects assessment of arthritis pain and physician global assessment of disease activity VAS scales, using the same approach as the sensitivity analysis on 4-component DAS28-hsCRP to identify the subjects to be included in this analysis set.

For the analyses on the other VAS-related secondary endpoints (ie, the individual assessments using VAS), using the same approach as the sensitivity analysis on 4-component DAS28-hsCRP, only subjects who completed the corresponding individual VAS assessment consistently will be included.

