4.5. Analysis Sets

The following analysis sets will be used:

Safety set: The Safety set is defined as all subjects who receive at least one dose of study drug (SKI-O-703 or placebo). Subjects will be analyzed as treated. This population will be used for summaries of safety data.

Intent-to-Treat (ITT) set: The ITT set is defined as all randomized subjects who receive at least one dose of study drug (SKI-O-703 or placebo). Subjects will be analyzed as randomized. This population will be used for all efficacy analyses and summaries of demographics and baseline characteristics data.

Modified Intention-to-Treat (mITT) set: The mITT set is defined as all the subjects who receive at least one dose of study drug (SKI-O-703 or placebo) and have at least 1 postbaseline assessment. Subjects will be analyzed as randomized. This population will be used for efficacy summaries and will include imputed data for subjects who withdraw from the study prior to the Week 12 visit.

Per Protocol (PP) set: The PP set is defined as all the subjects in ITT set who don't have any major protocol deviation(s) which will be flagged in the protocol deviation list and be compliant with the treatment as defined in [Section 7.2.2](#). All the efficacy analyses will be repeated on PP set. Subjects will be analyzed as randomized.

Pharmacokinetic (PK) set: The PK set will consist of all subjects who receive SKI-O-703 and have at least 1 measurable plasma concentration. Subjects who have partial data and/or major protocol deviations that may impact PK, and subjects who experience emesis, will be evaluated on a case-by-case basis and may be excluded from the PK population. This population will be used for summaries of PK data.

Pharmacodynamic (PD) set: The PD set will consist of all subjects who receive at least 1 dose of study drug (SKI-O-703 or placebo) and have at least 1 evaluable postdose PD value. Subjects who have partial data and/or major protocol deviations that may impact PD will be evaluated on a case by case basis and may be excluded from the PD population. This population will be used for summaries of PD data

Pharmacokinetic (PK)/pharmacodynamic (PD) set: The PK/PD set will consist of all subjects included in both the PK and PD populations. This population will be used for the PK/PD analyses.

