8.3. Secondary Efficacy Endpoints

8.3.1. Primary Analysis

The primary analysis will be conducted on observed cases without any imputation. All the secondary efficacy endpoints will be summarized and analyzed by treatment group at each schedule visit (Week 2, 4, 8, and 12) based on the ITT set and then repeated on the PP set.

The DAS28-related secondary endpoint is based on 3 individual components including TJC28, SJC28 and hsCRP (see calculation in [Section 8.1.1](#)). The analyses on ACR responses (ACR20, ACR50 and ACR70) will be restricted to subjects who completed subject global assessment of disease activity consistently, as well as physician global assessment of disease activity and subject assessment of arthritis pain, using the same approach as the sensitivity analysis on 4-component DAS28-hsCRP to identify the subjects to be included in the analysis. Similar to the

analyses on ACR responses, the analyses on the individual component using VAS will be restricted to subjects who completed the corresponding individual VAS assessment.

Frequency counts and percentages will be provided for ACR responses (ACR20, ACR50, and ACR70) at each schedule visit. The Chi-square tests will be used to compare the ACR response rate between each of active treatment group and placebo group, and among active treatment groups at each schedule visit. The p-values from the Chi-square tests will be presented. In case of few responders where Chi-square test may not be appropriate or accurate, Fisher's exact test will be performed instead. Besides, 95% CI of binomial proportion of ACR response within each treatment group and 95% CI of the difference in proportion of subjects with ACR response for pairwise treatment comparison will be estimated using the Wald method.

The hsCRP will be summarized descriptively by treatment group over schedule visits. No inferential statistics will be provided.

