8.4. Other Efficacy Endpoints

Based on the DAS28-hsCRP (based on 3 components including TJC28, SJC28 and hsCRP), we will evaluate if the subject achieves the following disease activity category at each schedule visit:

- DAS28-hsCRP ≤ 3.2
- DAS28-hsCRP < 2.6

The frequency counts and percentages of above DAS28 binary endpoints will be provided by treatment group at each schedule visit based on the ITT set and the PP set. The Chi-square tests will be used to compare the response rate between each of active treatment groups and placebo group, and among different active treatment groups. Besides, 95% CI of binomial proportion of ACR response within each treatment group and 95% CI of the difference in proportion of subjects with ACR response for pairwise treatment comparison will be estimated using the Wald method.

The analyses will also be analyzed based on the mITT set, where NRI method will be used to impute missing value. If at least 1 of the 3 components (TJC28, SJC28 and hsCRP) is non-missing at the given visit and the subject is still enrolled in the study, then use LOCF method to fill in any missing values for the 3 components. Then calculate the DAS28-hsCRP and evaluate the DAS28 binary endpoints as defined above. If all the individual components are missing at the given visit or if prior to the visit the subject is considered discontinued from the treatment, assign the subject as a non-responder.

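### Nonresponder imputation is run only on the mITT set, so a dosed subject with no postbaseline assessment at all is in no ACR or DAS28-category denominator

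*SAP*

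**What the plan says.** SAP 4.5 defines the two sets. For ITT: "The ITT set is defined as all randomized subjects who receive at least one dose of study drug". An mITT subject must be dosed "and have at least 1 postbaseline assessment". Neither the type nor the visit of that assessment is named.

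For the secondary endpoints on ITT, SAP 8.3.1 states: "The primary analysis will be conducted on observed cases without any imputation". The opening text of SAP 8 adds that a postbaseline summary includes only subjects with a value both at baseline and at that visit.

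NRI appears in three places, each time on mITT:
- Protocol 7.7.4: the ACR endpoints "will be also analyzed using the mITT set, where results for subjects that are missing at the relevant visit will be imputed using nonresponder imputation".
- SAP 8.3.2, for ACR20/50/70: "The ACR responses will also be analyzed based on the mITT set, where NRI method" is then applied to missing values.
- SAP 8.4, for the DAS28-hsCRP categories ≤3.2 and <2.6: "The analyses will also be analyzed based on the mITT set, where NRI method will be used to impute missing value".

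SAP 8.4 also gives a rule for the categories. A subject whose components are all missing at a visit, or who had already stopped treatment, is classed as a non-responder.

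**The concern.** NRI is meant to keep treated subjects in the denominator and to count those without an outcome as failures. A postbaseline value is needed to carry an observation forward, which is the other use of the mITT set (SAP 8.2.2). It is not needed to assign non-response. Tying NRI to mITT therefore removes the subjects who were dosed and never seen again, and the observed-case ITT analysis cannot recover them.

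The stake is the ACR and DAS28-category response rates and their unadjusted two-sided 5% comparisons with placebo. An arm that loses such subjects shows a higher rate than it would if all its dosed subjects were counted. The first scheduled postbaseline visit is Day 14 (protocol Table 6-1), so there is a window in which this can happen.

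**Working it through.** **Tracing one subject.** Take a subject who is randomized, takes one dose and has no later assessment.

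| Responder analysis | Set | Counted? | Reason |
|---|---|---|---|
| ACR, SAP 8.3.1 | ITT, observed | No | No value at the visit |
| ACR with NRI, SAP 8.3.2 | mITT | No | No postbaseline assessment |
| DAS28 categories, SAP 8.4 | ITT | No | General inclusion rule in SAP 8; 8.4 does not repeat the observed-case wording |
| DAS28 categories with NRI, SAP 8.4 | mITT | No | No postbaseline assessment |
| PP repeats | Subset of ITT | No | No value at the visit |
| ACR subgroups, SAP 8.5 | ITT, no NRI stated | No | No value at the visit |

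The multiple imputation in SAP 8.2.3 and 8.2.4 uses the full ITT set, but only for the continuous DAS28 components of the primary endpoint. It is not carried into a responder analysis.

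**Arm size.** The plan needs 37 completers per arm and allows 10% dropout (SAP 4.3). 37 / 0.90 = 41.1, rounded up to 42. Then 4 × 42 = 168 = 148 + 20, which reproduces the plan's enrolment ceiling. The documents give no ACR rate and no count of subjects without a postbaseline assessment.

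**Effect on one arm.** With r responders among N dosed subjects, k of them never assessed, NRI gives r/N on ITT and r/(N − k) on mITT. The excess is (r/N) × k/(N − k). For N = 42 and k = 1:
- r = 21: 21/41 − 21/42 = 51.2% − 50.0% = 1.2 points.
- r = 10: 10/41 − 10/42 = 24.4% − 23.8% = 0.6 points.

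**Effect on the difference.** Assumed: 21 responders on active, 10 on placebo, and k from 0 to 4 per arm (4 is about the whole 10% dropout). P-values are from the uncorrected chi-square test.

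| k active / placebo | Active | Placebo | Difference, points | Shift | p |
|---|---|---|---|---|---|
| 0 / 0 (same as ITT NRI) | 21/42 | 10/42 | 26.19 | 0 | 0.013 |
| 1 / 1 | 21/41 | 10/41 | 26.83 | +0.64 | 0.012 |
| 2 / 2 | 21/40 | 10/40 | 27.50 | +1.31 | 0.012 |
| 4 / 4 | 21/38 | 10/38 | 28.95 | +2.76 | 0.010 |
| 4 / 0 | 21/38 | 10/42 | 31.45 | +5.26 | 0.004 |
| 0 / 4 | 21/42 | 10/38 | 23.68 | −2.51 | 0.030 |

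**Near the 5% threshold**, with counts chosen to show both directions:
- 18 vs 10 responders: ITT NRI p = 0.064. Omitting 2 active subjects gives 18/40 vs 10/42, p = 0.043.
- 19 vs 10 responders: ITT NRI p = 0.039. Omitting 4 placebo subjects gives 19/42 vs 10/38, p = 0.079.

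**The case against.** The strongest reply is that few subjects are affected. Protocol 4.2.2 asks subjects who stop drug but stay in the study to complete an end-of-treatment visit, preferably within 2 weeks, and then to follow the visit schedule. Whenever possible, anyone who stops or withdraws has end-of-study assessments. Since mITT names no type of assessment, attending any such visit puts the subject in mITT, where NRI can count them as a failure. This stands. A reader might infer that early dropouts in general are never counted as non-responders; the documents support this only for subjects with no postbaseline assessment at all.

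A reader might also infer that the omission favours active drug, because early loss could come from intolerance. Gastrointestinal effects are listed as a potential risk (protocol 1.5), but nothing in the documents shows that loss before a first assessment would be dose-related, and placebo-side loss narrows the difference.

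A third tempting step is to charge the whole gap between observed-case and ITT NRI results to the mITT restriction. Suppose 18 of 42 respond and 4 drop out, 2 of them never assessed. The rates are 18/38 = 47.4% observed, 18/40 = 45.0% with NRI on mITT and 18/42 = 42.9% with NRI on ITT. Of the 4.5-point gap, 2.4 points are already handled by the planned NRI analysis. Only 2.1 come from the choice of set.

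The gap is also visible. SAP 5.1 reports ITT and mITT counts by arm, and omitted subjects cannot be responders. For the DAS28 categories, a reader can divide the mITT NRI responders by the ITT count. That recovers the rate, but the matching interval and test are not planned.

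Finally, these are secondary and other endpoints, and protocol and SAP agree with each other on the set.

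**Conclusion.** The gap is real but narrow: no planned ACR or DAS28-category analysis includes a dosed subject who has no postbaseline assessment. At an assumed 42 per arm, each such subject raises that arm's rate by about 1 point. In the scenarios above, the treatment difference moves by 0.6 to 2.8 points when 1 to 4 are lost equally in both arms, and by +5.3 or −2.5 points when 4 are lost only on active or only on placebo. Responder counts, k and its split between arms are assumptions. A change of significance needs a borderline result and uneven loss.

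A reader should not infer that the primary endpoint shares the gap: it is continuous and has a multiple-imputation sensitivity analysis on the full ITT set.

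The detailed ACR imputation rules are in protocol Appendix 13.4, which was not in the text reviewed. The analysis set is fixed by SAP 4.5 and 8.3.2 and protocol 7.7.4. That NRI can work without a postbaseline value is shown by the rule in SAP 8.4.

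**What to change.** In SAP 8.3.2 and 8.4 and protocol 7.7.4, run NRI on the ITT set, so that a dosed subject with no postbaseline assessment counts as a non-responder at every visit.

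For ACR, keep the restriction to consistent VAS completion, but state that having no postbaseline VAS is not by itself inconsistent completion. Otherwise the restriction could remove the same subjects again. Subjects whose VAS scoring really was inconsistent will still be excluded, so the ACR denominator will not be every dosed subject.

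The cost is a wording change and a population flag on two sets of tables, made before database lock, with no new data. Response rates may be slightly lower; if no such subjects exist, the results do not change. Making this the lead ACR analysis is a matter of preference and is not needed to close the gap.

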8.4. Other Efficacy Endpoints

Based on the DAS28-hsCRP (based on 3 components including TJC28, SJC28 and hsCRP), we will evaluate if the subject achieves the following disease activity category at each schedule visit:

- DAS28-hsCRP ≤ 3.2
- DAS28-hsCRP < 2.6

The frequency counts and percentages of above DAS28 binary endpoints will be provided by treatment group at each schedule visit based on the ITT set and the PP set. The Chi-square tests will be used to compare the response rate between each of active treatment groups and placebo group, and among different active treatment groups. Besides, 95% CI of binomial proportion of ACR response within each treatment group and 95% CI of the difference in proportion of subjects with ACR response for pairwise treatment comparison will be estimated using the Wald method.

The analyses will also be analyzed based on the mITT set, where NRI method will be used to impute missing value. If at least 1 of the 3 components (TJC28, SJC28 and hsCRP) is non-missing at the given visit and the subject is still enrolled in the study, then use LOCF method to fill in any missing values for the 3 components. Then calculate the DAS28-hsCRP and evaluate the DAS28 binary endpoints as defined above. If all the individual components are missing at the given visit or if prior to the visit the subject is considered discontinued from the treatment, assign the subject as a non-responder.

8.5. Subgroup Analysis

The focus of subgroup analysis will be limited to the baseline characteristics as listed below and the subgroup analysis will be conducted based on the ITT set for all the secondary efficacy endpoints specified in [Section 3.2.2](#). For VAS-related secondary endpoints (ACR responses and individual VAS assessments), the subgroup analysis will be restricted to subjects who completed the corresponding related VAS assessment consistently, same approach as described in the [Section 8.3.1](#) to identify the subjects to be included in the analyses.

- Number of previous csDMARDs treatments (0–2 csDMARDs, ≥ 3 csDMARDs)
- Previous anti-TNF α biologic agents use (Yes or No)
- Specific geographic region (APAC, EMEA, NA)

For ACR response endpoints, the number and percentage of responder and 95% Wald CIs will be provided by visit for each subgroup. The p-value of treatment comparison will be estimated by Chi-square tests within each subgroup. If all the subjects within a subgroup are responders or non-responders at a visit, only frequency counts and percentages will be provided for that subgroup and visit.

For other efficacy endpoints, the descriptive statistics of baseline, absolute value and change from baseline will be summarized by treatment group, scheduled visit and subgroup. By using the MMRM analysis as described in [Section 8.3.1](#), for each subgroup, the inferential statistics for treatment effect estimation and treatment comparisons will be provided by visit. In addition, subgroup comparison within treatment group will be provided as well by using a MMRM

analysis, which will be fitted with treatment group, subgroup, visit, treatment by visit interaction, treatment by subgroup interaction and baseline as fixed effects, and visit within subject as a repeated effect.

If too few subjects fall in the subgroup, the analysis within the subgroup may not be performed and only descriptive summary will be presented.

9. Safety Analysis

All the Safety analyses will be based on the Safety set.

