7.6 Description of Subgroups to be Analyzed

The primary and secondary endpoints described in Section 7.1 and Section 7.2 will be repeated for the following subgroups:

- The number of previous csDMARDs treatments (0~2 or ≥ 3)
- Previous 1, 2 or more anti-TNF α biologic agents use (Yes or No)
- Specific geographic region (APAC, EMEA, and NA)

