For all other secondary efficacy endpoints, descriptive statistics of baseline, observed value and change from baseline at each schedule visit will be provided by treatment group. Treatment comparisons will be conducted using a mixed model repeated measure (MMRM) analysis, including all the scheduled visits up through Week 12. The model will be fitted with treatment group, visit, treatment by visit interaction and baseline as fixed effects, and visit within subject as a repeated effect, using an unstructured covariance to model the between- and within-subject errors. If the model fails to converge with unstructured covariance matrix, use the heterogeneous Toeplitz covariance structure, followed by the heterogeneous autoregressive covariance, followed by the compound symmetry covariance structure. The inferential statistics from this model, including within-group LS means and the associated SE, treatment differences in LS means and the associated SEs, the 2-sided 95% CIs, the 2-sided p-values for treatment comparisons between each of active treatment group and placebo, and the 2-sided p-values for treatment comparisons among different active treatment groups (high dose vs. low dose) will be provided.

Listings for ACR responses, DAS28-hsCRP assessments, number of tender and swollen joints, subject assessment of pain using VAS, subject and physician global assessment of disease activity and HAQ-DI will be provided.

Plots of LS mean change from baseline in continuous primary and secondary efficacy endpoints by visit will be provided as well. Proportion of subjects with ACR response will be plotted by visit.

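### SAP 8.5 never contrasts active minus placebo between subgroups, and its additional MMRM holds the subgroup terms constant over Weeks 2 to 12

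*SAP*

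**What the plan says.** For continuous endpoints, SAP 8.5 plans two things.

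- **Treatment effects within subgroups.** The section 8.3.1 MMRM is applied so that "for each subgroup, the inferential statistics for treatment effect estimation and treatment comparisons will be provided by visit". In that base model, "The model will be fitted with treatment group, visit, treatment by visit interaction and baseline as fixed effects", "using an unstructured covariance to model the between- and within-subject errors", with a list of simpler structures if it does not converge.
- **Subgroups within arms.** In addition, "subgroup comparison within treatment group will be provided as well by using a MMRM". The fixed effects are treatment group, subgroup, visit, "treatment by visit interaction, treatment by subgroup interaction and baseline as fixed effects", with visit within subject as the repeated effect. Neither subgroup by visit nor treatment by subgroup by visit is listed.

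No interaction estimate, interaction p-value or between-subgroup contrast of active minus placebo is listed as output at any visit. For ACR responses there are chi-square tests within each subgroup only.

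The factors are number of previous csDMARDs (two levels), prior anti-TNFα use (two levels) and region (three levels). SAP 4.4 also uses them as randomization strata. On scope, the SAP says "subgroup analysis will be conducted based on the ITT set for all the secondary efficacy endpoints", while Protocol 7.6 says "The primary and secondary endpoints described in Section 7.1 and Section 7.2 will be repeated for the following subgroups". Week 12 DAS28-hsCRP is still covered under the SAP because it is also a secondary endpoint, but by MMRM and not by the primary ANCOVA.

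**The concern.** The question for which subgroup results are usually read is whether the drug effect, active minus placebo, differs between subgroups. A difference between subgroups inside one arm does not answer it. If patients with prior anti-TNFα failure do worse whatever they receive, the within-arm difference is large although the drug effect is the same in both groups. If prognosis and effect modification point in opposite directions, it can be close to zero when the drug effect differs.

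The second issue is time. Week 12 is the primary time point. The base MMRM lets the treatment effect change from visit to visit, but the additional model does not give the subgroup terms the same freedom. A subgroup difference read from it as a Week 12 result is in fact a weighted average over Weeks 2, 4, 8 and 12.

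What is at stake is the reading of the trial's own stratification factors. Protocol 3.1.2 says the results will guide further clinical evaluation. With no multiplicity adjustment (SAP 8), within-arm p-values and separate within-subgroup p-values are easy to misread as evidence about heterogeneity.

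**Working it through.** **Inputs from the documents.** Four arms of 37 completers, SD 1.25, difference 0.8, two-sided 0.05 (SAP 4.3); analyses "at each schedule visit (Week 2, 4, 8, and 12) based on the ITT set"; about 70/30 csDMARD to biologic (Protocol 3.1), taken here as 26/11 per arm of 37.

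**Inputs assumed.** The documents give no correlation between visits, no SD by visit and no time course of heterogeneity. I used compound symmetry (CS) with correlation 0.6 and AR(1) with 0.75, either with SD 1.25 throughout or with SDs 0.80, 1.00, 1.15, 1.25, and complete data.

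**Step 1: the plan's own figure.** Section 8.5 states none. The design figure reproduces: a one-way ANOVA F test with four groups, one differing by 0.8, SD 1.25, has power 0.794 at 36 per arm and 0.806 at 37. With 10% dropout, 37/0.9 rounds up to 42, and 42 × 4 = 168 = 148 + 20.

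**Step 2: what the additional model can estimate.** Write γ for the subgroup main effect and δ for the treatment-by-subgroup term of one active arm.

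- Subgroup difference within placebo: γ.
- Subgroup difference within that active arm: γ + δ.
- Difference in active minus placebo between subgroups: (γ + δ) − γ = δ.

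Neither γ nor δ carries a visit index, so all three contrasts have the same coefficients at Weeks 2, 4, 8 and 12. The treatment effect does vary, through treatment by visit. For a two-level factor, baseline aside, the model has 1 + 3 + 1 + 3 + 9 + 3 = 20 parameters for 4 × 2 × 4 = 32 cell means. The missing 12 are subgroup by visit (3) and treatment by subgroup by visit (9). For region the counts are 24 and 48.

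**Step 3: what the single δ averages.** With covariance Σ over the four visits, the GLS weights are w = Σ⁻¹1 / (1′Σ⁻¹1), and the expected estimate is Σ w(t) h(t), where h(t) is the true heterogeneity at week t as a fraction of its largest value.

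- Linear growth: h = 2/12, 4/12, 8/12, 1.
- Fading: h = 1, 0.8, 0.4, 0, so the true Week 12 value is 0.

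| Assumed covariance | Weights, Weeks 2, 4, 8, 12 | Linear growth | Fading |
|---|---|---|---|
| CS 0.6, equal SD | 0.25, 0.25, 0.25, 0.25 | 0.54 | 0.55 |
| AR(1) 0.75, equal SD | 0.40, 0.10, 0.10, 0.40 | 0.57 | 0.52 |
| CS 0.6, rising SD | 0.77, 0.24, 0.04, −0.05 | 0.19 | 0.98 |
| AR(1) 0.75, rising SD | 0.86, −0.04, 0.01, 0.16 | 0.30 | 0.84 |

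First row: 0.25 × (2 + 4 + 8 + 12)/12 = 0.54. Second row: 0.40 × 2/12 + 0.10 × 4/12 + 0.10 × 8/12 + 0.40 = 0.57. Rising SDs move the weight to the early visits.

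For a heterogeneity of 0.80 at Week 12 reached linearly, the model returns 0.43, 0.45, 0.15 and 0.24 in the four rows. For one that fades from 0.80 at Week 2 to 0 at Week 12, it returns 0.44, 0.42, 0.78 and 0.67.

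**Step 4: sensitivity to the assumptions.**

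- Constant heterogeneity: the weights sum to 1, so the model recovers 100%.
- Early plateau (40, 70, 90, 100% at the four visits): 72-75% with equal SDs, 46-49% with rising SDs.
- Milder SD rise (1.10, 1.15, 1.20, 1.25), linear growth: 42-48%.
- CS 0.7 with the 0.80 to 1.25 rise, linear growth: weights 0.93, 0.24, −0.03, −0.14, recovery 8%. So 19-30% is an illustration, not a bound.

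**Step 5: after adding the two terms.** The Week 12 contrast is free and is recovered exactly in each scenario run. Its precision, taking SD 1.25 at Week 12:

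- 26/11 split: SE = 1.25 × √(2/26 + 2/11) = 0.64; detectable with 80% power 0.636 × (1.960 + 0.842) = 1.78; power for 0.8 is Φ(0.8/0.636 − 1.960) = 0.24.
- 50/50 split: SE = 1.25 × √(4/18.5) = 0.58; detectable 1.63; power 0.28.

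**The case against.** The strongest reply is that the first analysis already gives active minus placebo at Week 12 in every subgroup, with SE and 95% CI and without any constancy restriction. If those are separate fits, the subgroups are disjoint, and a reader can subtract two estimates and combine the SEs as the root of the sum of squares. That stands. What is missing is one explicit contrast, not Week 12 subgroup information altogether.

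The sponsor can also say that the additional model is labelled as a comparison within treatment group and is not presented as an estimate of heterogeneity. That stands too. A reader might infer that the SAP will report prognostic differences as effect modification; nothing in it says so. A reader might also infer that the model forces a constant treatment effect over visits; it does not, because treatment by visit is included.

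Finally, the size of the error is assumption-driven and not one-directional, the analyses are supportive, and an interaction of 0.8 has power of only about 0.24 to 0.28. All true. Low power favours an interval labelled exploratory. It does not make the within-arm comparison, or two p-values set side by side, answer the heterogeneity question.

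**Conclusion.** The concern holds as a gap in the subgroup outputs and a restriction in the additional model. Treatment effects are reported by visit within subgroups but never contrasted between them. The model that does compare subgroups does so within an arm, and its subgroup difference and treatment-by-subgroup term are fixed over visits. The latter equals the Week 12 heterogeneity only if heterogeneity is constant over visits; likewise, the within-arm difference equals its Week 12 value only if that difference is constant.

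The absence of the two terms is a matter of text and algebra. The magnitude is not: it rests on assumed covariances, assumed time courses and complete data. A claim that the plan will understate heterogeneity is therefore too strong, since that happens when heterogeneity builds with time and the reverse happens when it fades. Nor do the documents support calling the additional model wrong for its stated, within-arm purpose. The Week 12 ANCOVA and primary inference are untouched. This is a cheap improvement.

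**What to change.** In SAP 8.5, add subgroup by visit and treatment by subgroup by visit to the additional MMRM. In addition to the planned outputs, report for each active dose the Week 12 difference in active minus placebo between subgroups, with its 95% CI, labelled exploratory. State that the within-arm comparisons are descriptive of prognosis and effect together.

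Where cells are too sparse to fit this, use a Week 12 ANCOVA with treatment by subgroup, or the descriptive fallback that SAP 8.5 already contains. Region is the likely case: 148/12 is about 12 subjects per region-by-arm cell on average.

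The cost is 12 extra parameters for a two-level factor and 24 for region, under an unstructured covariance where it converges, and intervals that will be wide (SE about 0.58 to 0.64). No new data are needed, and the change can be made before database lock.
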